5.2.3 Dietary Patterns

Healthful dietary patterns are essential for the management of T2DM, and are the mechanism through which A1C improves or declines.⁶² We used both subjective and objective measurements to provide a comprehensive assessment of the quality of participants' dietary patterns.

Dietary Intake We collected self-reported (i.e., subjective) dietary intake data to assess the quality of dietary patterns using the ASA24-2018-Canada online system, which is a modified version of the ASA24 based on the Canadian food supply, portion sizes, and nutrition composition.⁶³ Participants reported all foods, beverages, and supplements consumed from midnight-to-midnight the previous day as well as if their reported intake was more than usual, usual, or less than usual. The system also recorded the date and time for each recall. Participants completed 2 x 24-hour dietary recalls for a total of 6 recalls to better capture the intake of episodically consumed foods and daily variability, thereby, providing more accurate estimates of usual dietary intake.

Prompts to enter a second recall were sent 2-5 days after the first recall, with the specific interval determined at random. Participants entered dietary recalls on any day of the week including weekends (Friday-Sunday). This data will be used to determine recall day and season of measurement, which is defined as spring (March-May), summer (June-August), autumn (September-November), and winter (December-February).

We will use this data to assess the alignment of participants' dietary intake with national nutrition guidance by using the appropriate scoring algorithms to calculate Healthy Eating Food Index 2019 (HEFI-2019)^{64, 65} and Healthy Eating Index-2015 (HEI-2015)⁶⁶⁻⁶⁹ scores. The HEFI-2019 is a 10-component index that aligns with the content and objectives of Canada's Food Guide 2019 (CFG-2019). Total HEFI-2019 scores are the sum of individual component scores, and range from 0-80 with higher scores indicating greater adherence to CFG-2019 guidelines.⁶⁴ The HEI-2015 is a 13 component index that sums component scores for adequacy (foods that align with nutritional guidelines) and moderation (foods with suggested limited intake), and a total score, which ranges from 0-100, with higher scores indicating higher adherence to the 2015-2020 Dietary Guidelines for Americans. For each index, scores will be calculated as the mean of two recalls when available; if only one recall is available, a single score will be used. HEFI-2019 and HEI-2015 scores will be analyzed as continuous outcomes.

*Ultra-Processed Foods** We will use dietary intake data collected with the ASA24-2018-Canada to calculate the proportion of energy consumed from ultra-processed foods (UPF), which are manufactured foods and beverages that contain few to no whole foods. All foods and beverages reported in dietary recalls will be classified using the NOVA classification system, which includes definitions and examples.⁷⁰ This system classifies foods and beverages into 4 groups, including unprocessed or minimally processed, processed culinary ingredients,

processed, or ultra-processed. The numerator for each group will be the average energy intake from UPF from both recalls and the denominator for all groups will be the total average daily energy intake from both recalls at each timepoint. UPF will be analyzed as a continuous outcome.

Skin Carotenoids Notwithstanding their demonstrated validity⁷¹, dietary recalls are subjective self-reports and are prone to reporting errors and bias.⁷² To address these issues, we collected skin carotenoid data to provide objective approximations of vegetable and fruit consumption, which are key components of healthy dietary patterns.⁷³ Carotenoids are phytonutrients only present in food and are abundant in vegetables and fruit. Once consumed, they are stored in both blood and skin. Skin carotenoids are valid and reliable measures of fruit and vegetable intake,⁷⁴ and are positively correlated with plasma carotenoids.⁷⁵ We measured carotenoids dermally using Pharmanex Biophotonic Scanners (NuSkin Enterprises, Provo, UT, USA), which are non-invasive measurements taken through participants' palms. Researchers collected 3 scans for each participant. Each scan provides a score ranging from 10,000 to 80,000, with 10,000 indicating a diet low in carotenoids and 80,000 indicating a diet very high in carotenoids.⁷⁶ Researchers collected 3 scans for each participant. Scores for each participant will be calculated by averaging these 3 measurements. Skin carotenoids will be analyzed as a continuous outcome.

*Supplements** Participants also reported dietary supplement intake in each recall. Evidence suggests consuming supplements containing carotenoids may substantially increase plasma and skin carotenoid levels.^{77,78} We will create a binary indicator variable to capture supplement intake. Intake is defined as consumption of supplements containing beta-carotene, lycopene, lutein, zeaxanthin, alpha-carotene, or gamma-carotene both individually and in combination. No intake is defined as consumption of supplements that do not include the aforementioned carotenoids or supplement consumption was not reported in the dietary recalls. Supplement intake will be included as a covariate to account for potential influence on observed skin carotenoid levels, thereby allowing estimates to better reflect consumed foods.

5.2.4 Patient Reported Outcomes

Household Food Insecurity

Household food insecurity, defined as inadequate or insecure access to food due to financial constraints,⁷⁹ was assessed using Health Canada's validated 18-item Household Food Security Survey Module (HFSSM).⁸⁰ We slightly modified the module to fit the study's data collection schedule. Response options were preserved in their original format, with the sole modification being a change in the reference period from 12 months to 6 months. Participants rated the frequency in which they 1) worried about running out of food for themselves and/or household members including children, 2) cut the size of their meals or skipped meals, and/or 3) went entire days without eating because there was not enough money for food. Response values range from 1 (never true) to 3 (often true) for primary questions, and 1 (only 1 or 2 weeks) to 3 (almost every week) for sub questions. Adults with children <18 years of age living in the home completed all 18 module questions. Adults with no children living in the home completed the 10 questions for adults only. Scoring is determined by the total number of affirmative responses, which are subsequently classified as food secure, marginally food insecure, moderately food insecure, or severely food insecure as described in Table 1.

We will assess the presence of household food insecurity as a binary variable by comparing those who were experiencing food insecurity (≥ 1 affirmative responses) to those who were food secure (0 affirmative responses). We will also assess the severity of household food insecurity as an ordinal variable by comparing those who experienced marginal, moderate, or severe food insecurity to those who were food secure.

Status	Interpretation	10 item adult food security scale	8 item child food security scale
Food secure	No report of income-related problems of food access.	No items affirmed	No items affirmed
Marginally food insecure	Some indication of worry or an income-related barrier to adequate, secure food access	Affirmed no more than 1 item on either scale	
Moderately food insecure	Compromise in quality and/or quantity of food consumed by adults and/or children due to a lack of money for food.	2 to 5 affirmative responses	2 to 4 affirmative responses
Severely food insecure	Disrupted eating patterns and reduced food intake among adults and/or children	6 or more affirmative responses	5 or more affirmative responses

Note: In cases where a household meets the condition of two different classifications (that is, different status on the child and adult scales), the household is given the more severe classification).

Table 1: Reproduced from PROOF⁴³ with permission and in accordance with licensing requirements.⁸¹

Diabetes Self-Efficacy

Diabetes self-efficacy was assessed using the validated 8-item Stanford Diabetes Self-Efficacy Scale, which measures self-reported confidence in completing activities related to diabetes management.^{82, 83} The questions query current feelings of confidence in completing activities for managing diabetes, including regular meals, choosing appropriate foods, regular exercise, and activities to promote glycemic control. Response values range from 1 (not at all confident) to 10 (totally confident). The total score is the mean of the responses to all questions with higher scores indicating more self-efficacy and lower scores indicating less self-efficacy. Diabetes self-efficacy will be analyzed as a continuous outcome.

Diabetes Self-Management

Diabetes self-management was assessed using the validated 16-item Diabetes Self-Management Questionnaire, which measures self-care behaviour.^{84, 85} The questions assess self-care behaviours associated with glycemic control for both type 1 and type 2 diabetes over the previous 8 weeks, including monitoring blood sugar levels, regular appointment attendance, adherence to medication regimen, and physical activity. Response values range from 0 (does not apply to me) to 3 (applies to me very much). Subscales include Glucose Management (items 1, 4, 6, 10, 12), Dietary Control (items 2, 5, 9, 13), Physical Activity (items 8, 11, 15), and Health-Care Use (items 3, 7, 14). Item 16 provides an overall rating of diabetes self-care. Scores will be calculated as sums of all item scores and then transformed to a scale with a range of 0 (lowest rating of self-care) to 10 (highest rating of self-care). A score of ≤6 indicates lower self-care. Diabetes Self-Management will be analyzed as a continuous outcome.

Diabetes Distress

Diabetes distress was assessed using the validated 5-item Problem Areas in Diabetes Scale (PAID5), which measures emotional distress related to diabetes.⁸⁶ The questions provide a rapid screening of current emotional distress due to diabetes, including fear, depression, worry, capacity, and coping. Response values range from 0 (not a problem) to 4 (serious problem). Possible scores range from 0-20 with higher scores suggesting greater diabetes-related emotional distress and lower scores indicating lower diabetes-related emotional distress. The total score will be calculated by summing responses for all questions. A total score of ≥8 indicates possible distress. Diabetes distress will be analyzed as a continuous outcome.

Diabetes Competing Demands

Diabetes competing demands was assessed using a 4-item scale purposively developed by Lorig et al (1996)⁸⁷, which measures frequency of delaying the purchase of necessities. The questions queried how often participants must make decisions between purchasing necessities for either daily life or diabetes management (e.g., food, medication, supplies) over the previous 6 months. Response values range from 1 (never) to 4 (always). A trade-off is considered to have occurred if a participant answers “often” or “sometimes” to either question. Diabetes competing demands will be analyzed as a binary outcome.

Perceived Financial Barriers to Chronic Disease Care

Perceived financial barriers to chronic disease care was assessed using 2 items from the Barriers to Care for People with Chronic Health Conditions survey.⁸⁸ The questions assessed the frequency of encountering difficulties purchasing necessities and supplies over the previous 6 months. Response values range from 1 (always) to 5 (never). Sub questions query specific services, equipment, or medication. Financial barriers are present if a participant answers always, often, or sometimes to either question. Perceived financial barriers to chronic disease care will be analyzed as a binary outcome (yes, no).

Hypoglycemic Episode Frequency

Frequency of hypoglycemic episodes (i.e., low blood sugar reaction so severe the participant required glucagon, physician support, or emergency assistance) in the previous 6 months was assessed using the validated single-item Hypoglycemic Episode tool.⁸⁹ Response values include 0 times, 1-3 times, 4-6 times, 7-11 times, and ≥ 12 times. Hypoglycemic episode frequency will be analyzed as an ordinal outcome.

Psychosocial Well-Being

Psychosocial well-being was assessed using the validated 5-item WHO Well-Being Index.^{90,91} The questions measure subjective well-being over the previous 2 weeks by querying positive mood, calm feelings, vigour, feeling well rested, and interest in daily life. Response values range from 0 (at no time) to 5 (all the time). Raw scores will be calculated by totaling answers from all questions, with a range from 0 (worst possible quality of life) to 25 (best imaginable quality of life). A percentage score will be calculated by multiplying the raw score by 4, with a range from 0% (worst possible well-being) to 100% (best possible well-being). A score of ≤ 50 suggests poor psychosocial well-being. Psychosocial well-being will be analyzed as a continuous outcome.

Quality-Adjusted Life-Years

Self-rated health was assessed using the validated European Quality of Life Five Dimension Five Level Scale (EQ-5D-5L).^{92,93} The questions measure current self-rated health across 5 dimensions including mobility, self-care, usual activities, pain/discomfort, and anxiety/depression. Response values range from 1 (no problems) to 5 (extreme problems), with one response selected for each domain. Health states can be reported descriptively as a 5-digit code, reflecting the level selected in each domain, or converted into a single index value using country-specific population-based preference weights.⁹⁴⁻⁹⁶ The index values represent 1.0 (full health) to 0.0 (death), with scores less than 0 representing states worse than death. Higher index values represent better health. We will use the Canadian Eq-5D-5L value set, specifically the model 4 scoring algorithm (combines both time trade-off and discrete choice experiment data), to calculate index values. These health-related quality-of-life scores will be used to estimate a quality-adjusted life-year (QALY) using an area under the curve approach.⁹⁷ The QALY will be analyzed as a continuous outcome.

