7.2 Covariate Adjustments, Subgroup Analyses, and Sensitivity Analyses

Models will be adjusted for baseline values of each outcome, blocking variables, and covariates specific to each outcome, which are described in the manuscript sections.

Subgroup analyses will be conducted for one outcome in each paper. These analyses are described in each manuscript section.

We will conduct per protocol sensitivity analyses for each outcome wherein data for participants who did not adhere to their assigned group will be removed from the analysis. We will also conduct as-treated sensitivity analyses for each outcome wherein participants will be analyzed based on their incentive usage by 1) using pre-specified cut points based on percentage of incentives redeemed (25%, 50%, 75%), 2) basing usage on weeks used wherein participants who earned the incentive ≥ 27 weeks will be analyzed as part of the FoodRx group and participants who earned the incentive ≤ 26 weeks will be analyzed as part of the comparison group, and 3) basing usage on incentive level by comparing single households to the remaining levels (i.e., 2+ households and above). Additional sensitivity analyses are described in each manuscript section.

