We will assess group differences in diabetes self management as a continuous outcome using mixed-effects linear regression. Models will be adjusted for baseline diabetes self management, and blocking variables (baseline A1C, gender, recruitment location). To improve the precision of effect estimates, models will also be adjusted for age, race/ethnicity, educational attainment, annual household income, years lived in Canada, household composition, marital status, and diabetes duration. Additionally, all models will include baseline A1C data source (study measured vs administrative health data), and group (FoodRx vs comparison) indicator variables. We will include random intercepts for participants (participant study ID) to account for within-subject correlation due to repeated measures, and for primary care clinics (clinic study ID) to account for clustering of participants within clinics. Missing data for covariates will be addressed using full information maximum likelihood.

In addition to per-protocol and as-treated analyses, we will conduct sensitivity analyses for diabetes self management as described in Section 7.2.

Diabetes Distress

We will assess group differences in diabetes distress as a continuous outcome using mixed-effects linear regression. Models will be adjusted for baseline diabetes distress, and blocking variables (baseline A1C, gender, recruitment location). To improve the precision of effect estimates, models will also be adjusted for age, race/ethnicity, educational attainment, annual household income, years lived in Canada, household composition, marital status, and diabetes duration. Additionally, all models will include baseline A1C data source (study measured vs administrative health data), and group (FoodRx vs comparison) indicator variables. We will include random intercepts for participants (participant study ID) to account for within-subject correlation due to repeated measures, and for primary care clinics (clinic study ID) to account for clustering of participants within clinics. Missing data for covariates will be addressed using full information maximum likelihood.

In addition to per-protocol and as-treated analyses, we will conduct sensitivity analyses for diabetes distress to examine the impact on results when diabetes distress is modelled as an ordinal outcome using mixed-effects logistic regression.

Diabetes Competing Demands

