We will assess group differences in diabetes competing demands as a binary outcome using mixed-effects logistic regression. Models will be adjusted for baseline diabetes competing demands, and blocking variables (baseline A1C, gender, recruitment location). To improve the precision of effect estimates, models will also be adjusted for age, race/ethnicity, educational attainment, annual household income, years lived in Canada, household composition, marital status, and diabetes duration. Additionally, all models will include baseline A1C data source (study measured vs administrative health data), and group (FoodRx vs comparison) indicator variables. We will include random intercepts for participants (participant study ID) to account for within-subject correlation due to repeated measures, and for primary care clinics (clinic study ID) to account for clustering of participants within clinics. Missing data for covariates will be addressed using full information maximum likelihood.

In addition to per-protocol and as-treated analyses, we will conduct sensitivity analyses for diabetes competing demands as described in Section 7.2.

Hypoglycemic Episode Frequency

We will assess group differences in hypoglycemic episode frequency as an ordinal outcome using mixed-effects logistic regression. Models will be adjusted for baseline hypoglycemic episode frequency, and blocking variables (baseline A1C, gender, recruitment location). To improve the precision of effect estimates, models will also be adjusted for age, race/ethnicity, educational attainment, annual household income, years lived in Canada, household composition, marital status, diabetes duration, and physical activity level. Additionally, all models will include baseline A1C data source (study measured vs administrative health data), and group (FoodRx vs comparison) indicator variables. We will include random intercepts for participants (participant study ID) to account for within-subject correlation due to repeated measures, and for primary care clinics (clinic study ID) to account for clustering of participants within clinics. Missing data for covariates will be addressed using full information maximum likelihood.

In addition to per-protocol and as-treated analyses, we will conduct sensitivity analyses for hypoglycemic episode frequency as described in Section 7.2.

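### The binary rule for diabetes competing demands leaves out *always*, so the worst and best response patterns share a code, and it does not say which of the four items count

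*SAP*

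**What the plan says.** SAP section 5.2.4, under Diabetes Competing Demands, makes three statements in one paragraph:

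- the instrument: "Diabetes competing demands was assessed using a 4-item scale";
- the response scale: "Response values range from 1 (never) to 4 (always");
- the coding rule: "A trade-off is considered to have occurred if a participant answers “often” or “sometimes” to either question".

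The next outcome in the same section, perceived financial barriers, has two items on a 5-level scale and this rule: "Financial barriers are present if a participant answers always, often, or sometimes to either question".

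Section 7.7 carries competing demands forward only in binary form: "We will assess group differences in diabetes competing demands as a binary outcome using mixed-effects logistic regression". It adjusts for the baseline value of the same variable and does not restate the coding. For sensitivity it says "we will conduct sensitivity analyses for diabetes competing demands as described in Section 7.2". Section 7.2 describes per-protocol analyses ("We will conduct per protocol sensitivity analyses for each outcome") and as-treated analyses based on incentive use.

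**The concern.** The rule names the two middle responses and omits the most severe one. The resulting variable does not rise steadily with severity: *never* is 0, *sometimes* and *often* are 1, and *always* goes back to 0. If every other counted item is *never* or *always*, a participant who improves from *always* to *often* on one item is scored as having acquired a trade-off.

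The rule also speaks of two questions although the scale has four items. The analyst must decide whether any of the four counts or only some pair.

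This coding is the only form in which the outcome is analysed, and the same coding supplies its baseline covariate. If the incentive helps the worst-off participants most, the literal rule works against it: people leaving *always* for a milder level enter the trade-off group. An analyst who spots the problem once data are in hand must either follow a rule that miscodes or depart from it after the fact.

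**Working it through.** **Inputs from the SAP.** Four items; four response levels from never to always; trade-off coded for *often* or *sometimes* (section 5.2.4). The labels of the two middle levels are taken from the rule itself. The SAP states no response distribution and no figure to reproduce, so the work is a check of logic followed by illustrations on assumed values.

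**Step 1: response patterns.** Count the patterns coded as a trade-off under the literal rule and under the rule with *always* added.

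| Counted items | All patterns | Literal rule | With *always* | Patterns that change |
|---|---|---|---|---|
| 2 | 4² = 16 | 16 − 2² = 12 | 16 − 1 = 15 | 3 |
| 4 | 4⁴ = 256 | 256 − 2⁴ = 240 | 256 − 1 = 255 | 15 |

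Every pattern that changes consists only of *always*, or of *always* and *never*. A participant with at least one *sometimes* or *often* on a counted item is coded correctly either way. With *always* included, counting any of four items gives 255 positive patterns and counting one fixed pair gives 240, so 15 patterns depend on which items count. These are counts of patterns, not proportions of participants.

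**Step 2: one counted item.** The literal proportion is P(any trade-off) − P(always). Hence

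literal risk difference (FoodRx − comparison) = true risk difference + (P(always) in comparison − P(always) in FoodRx).

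A true benefit shrinks when *always* is lower in the FoodRx arm. It changes sign only if that gap exceeds the gap in any trade-off.

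Assume any trade-off of 50% in the comparison arm and 45% in the FoodRx arm. True OR = (0.45/0.55)/(0.50/0.50) = 0.82. Odds ratios under the literal rule, where *falls* means lower in the FoodRx arm than in the comparison arm:

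| *Always* in comparison arm | Falls by 10% (proportional) | Halves | Falls by two thirds |
|---|---|---|---|
| 2% | 0.82 | 0.85 | 0.86 |
| 5% | 0.83 | 0.90 | 0.93 |
| 10% | 0.84 | 1.00 | 1.07 |
| 15% | 0.85 | 1.11 | 1.24 |

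Three cells in full:

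- 15% to 5%: 0.50 − 0.15 = 0.35 against 0.45 − 0.05 = 0.40; OR = (0.40/0.60)/(0.35/0.65) = 1.24.
- 10% to 5%: 0.40 against 0.40; OR = 1.00. This is the break-even point, with both gaps equal to 5 points.
- 15% to 13.5%: 0.35 against 0.315; OR = (0.315/0.685)/(0.35/0.65) = 0.85.

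**Step 3: four counted items.** Assume each item in the comparison arm is 15% *always*, 35% *often* or *sometimes*, and 50% *never*.

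- Independent items: any *always* = 1 − 0.85⁴ = 47.8%; miscoded = 0.65⁴ − 0.50⁴ = 11.6% of the arm, or 11.6/47.8 = 24% of those with any *always*.
- Items in full agreement: 15% of the arm miscoded, which is everyone with any *always*.
- Correlated items (ordinal probit, equal latent correlation): at 0.5, any *always* 35.8% and miscoded 5.3% (15% of them); at 0.7, 30.3% and 5.0% (17%).

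With each FoodRx item at 45% any trade-off:

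| Latent correlation | True OR | Literal OR, *always* falls by 10% | Literal OR, *always* falls by two thirds |
|---|---|---|---|
| 0.5 | 0.78 | 0.80 | 1.01 |
| 0.7 | 0.80 | 0.82 | 0.97 |

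**Step 4: would a planned analysis show it?** The section 7.2 analyses change who is included or which group they are placed in; they keep the outcome coding. Diabetes distress has an analysis that varies the form of the outcome (section 7.7: "the impact on results when diabetes distress is modelled as an ordinal outcome"). Competing demands has none.

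**The case against.** The omission is probably a drafting slip. The neighbouring rule includes *always*, the outcome is meant to record whether a trade-off occurred, and section 4.4 promises an audit file for data cleaning, so an analyst might well code it sensibly. That is plausible, but it does not repair the text: this is the only coding definition in the SAP text available.

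Which statement is wrong cannot be settled from the document. The item wording is not shown, and if the *always* anchor is the misdescribed part, nobody is miscoded. This stands. The inconsistency is certain; the miscoding is conditional on a literal reading with the scale as stated. Section 7.1 also points to an Appendix A listing outcomes and variables. It is not in the text available, so whether it defines the coding could not be checked.

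The illustrative inputs are invented, and reversal needs *always* to fall by more, in percentage points, than any trade-off does. Under a proportional fall the odds ratios barely move, and with four correlated items even a two-thirds fall gives roughly a null result, not a clear reversal. The odds ratios are also unadjusted, whereas the planned model is mixed-effects and conditions on baseline. All of this is fair and limits what can be said about size.

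The comparators are imperfect. Financial barriers is a different instrument with a 5-level scale in reverse order, and distress is a summed score. They suggest how the rule could be worded and what kind of analysis would expose the problem, but they do not prove what was intended.

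**Conclusion.** The concern holds. As written, the rule contradicts the response scale in its own paragraph, gives the most and least severe response patterns the same code, and does not fix which items count.

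The number of participants affected is unknown. Under the assumed distributions above, the consequence ranges from almost none to loss or reversal of a modest benefit, depending on how common *always* is, how much it differs between arms, and how strongly the items agree. The bias runs against the intervention when *always* is less frequent in the FoodRx arm.

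The reach is limited. Section 6.5 presents secondary outcomes as exploratory, and the 12-month A1C analysis does not depend on this variable. It should still be corrected before analysis, because deciding afterwards whether *always* counts, or which items count, would be a choice made with the results in view.

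**What to change.** Before the outcome is analysed, amend section 5.2.4 as follows:

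1. Reconcile the rule with the scale. Either state that *sometimes*, *often* and *always* all count as a trade-off, in line with the financial-barriers rule, or correct the scale anchor if that is what was misdescribed.
2. Replace the reference to two questions with any of the four items, or name the items that count.
3. State that the same coding applies at baseline and at follow-up, since the baseline value is a covariate in the section 7.7 model.

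The cost is one or two sentences in the SAP. No new data are needed.
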